4.6 Questionnaires

Unless otherwise indicated, some of the assessments below may be completed multiple times across the participant's inpatient stay to assess any effect of diet.

Profile of Mood States (POMS) Questionnaire: The Profile of Mood States (POMS) is a widely used questionnaire for measuring distinct mood states. The POMS has 65 items, each with a 5-point adjective rating scale, which measures six identifiable moods or feelings "over the past week, including today": Tension-Anxiety (T), Depression-Dejection (D), Anger-Hostility (A), Vigor-Activity (V), Fatigue-Inertia (F) and Confusion-Bewilderment (C). Completion of the POMS takes 5-10 minutes. DSM-5 Self-Rated Level 1 Cross-Cutting Symptom Measure: This questionnaire is delivered during the screening visit and assesses mental health domains that are

important across psychiatric diagnoses. It consists of 23 questions that assess 13 psychiatric domains, including:

- Depression
- Anger
- Mania
- Anxiety
- Somatic symptoms
- Suicidal ideation
- Psychosis
- Sleep problems
- Memory
- Repetitive thoughts and behaviors
- Dissociation
- Personality functioning
- Substance use

Each item asks about how much (or how often) the individual has been bothered by the specific symptom during the past 2 weeks. Each item on the measure is rated on a 5-point scale. Cutoff scores, critical items, and follow-up measures are provided for each disorder. The questionnaire will be scored by a qualified member of the study team immediately after completion. If the subject scores above the cutoff for one or more disorders, these results will be discussed with a medically qualified team member, and a Clinical Center psychiatry consult will be obtained as appropriate.

Food Frequency Questionnaires (FFQ): Food Frequency Questionnaires (FFQ) are self-assessment questionnaires developed to identify foods and macronutrients that significantly contribute to energy intake [23]. Subjects will be given instructions to complete a form, which will be reviewed for completeness by clinic staff and any blank answers will be resolved. The FFQ contains questions on the frequency and portion size of consumption of certain food items over a defined period of time.

Three-Factor Eating Questionnaire: The three-factor eating questionnaire (TEFQ) is a self-assessment questionnaire developed to measure dietary restraint, disinhibition and hunger [24]. The questionnaire contains 36 items with a yes/no response, 14 items with a 1-4 response scale and 1 item with a 1-5 response scale.

MacArthur Socioeconomic Status (SES) Questionnaire: The MacArthur SES questionnaire is a widely used self-assessment questionnaire. It begins with subjective social status questions, followed by questions assessing educational attainment, occupational status, income and assets.

Hunger & Satiety Assessment: At several time points throughout the study, subjects will be asked to complete a survey to identify their perception of hunger (i.e., visual analog scale [VAS]) [22]. More specifically, the VAS survey will consist of four questions: 1) "How hungry do you feel right now?" 2) "How full do you feel right now?" 3) "How much do you want to eat right now?" and 4) "How much do you think you can eat right now?" Below each question on the survey there is a horizontal 100mm line with qualifying statements such as "Not at all"/"The

least I can possibly" and "Extremely"/"The most I can possibly", anchoring the line on the extreme left and right side, respectively. In response to each question, subjects will be asked to draw a vertical mark on the horizontal line to represent the magnitude of their response to the question. A value for each response is quantified by measuring the distance of their mark (in mm) relative to the left end of the line. Therefore, the values (or "scores") for each question range from 0 to 100. On a few select days, data will be collected at least every 30 to 60 minutes over the next 2-3 hours after consuming each of their meals. It will take approximately 3 minutes for a participant to complete the assessment at a given time.

Sensory and palatability assessments: On several days throughout the study, subjects will be asked to complete a survey to assess the palatability and sensory properties (such as taste, texture, etc.) of the meals provided. Subjects will complete 100-point VAS line scale ratings of a series of measures, including meal liking and selected sensory properties. Survey items will be completed before eating, after the first bite, and after the participant has finished eating. Ratings include: how filling they expect a meal to be (expected fullness), how quickly or slowly they felt they ate the meal, and the extent to which they feel hungry, full and thirsty, their desire to eat and prospective consumption. The scale responses range from "Not at all" (0) to "Very" (100), except for prospective consumption, which is anchored by "Nothing at all" (0) and "The most I have ever eaten" (100). These ratings will be embedded amongst distracter "mood" ratings of alert, happy, and clear-headed. It will take approximately 3 minutes for a participant to complete the assessment at a given time.

Self Reported Habit Index. 12-item self-report instrument of habit strength (the Self-Report Habit Index. SRHI is a reliable and valid instrument. It measures habit strength by breaking it down into a number of features of habit; that is, history of repetition, automaticity (lack of control, lack of awareness, efficiency), and expression of one's identity.

Satisfaction with life, Happiness and Well Being scales. Satisfaction with Life Scale includes 5 items that assess general (e.g., my life is going well) aspects of subjective well-being.

UPPS-P Impulsive Behavior Scale: The UPPS-P is a 59-item self-report questionnaire used to assess impulsivity based on five subscales: urgency, premeditation, perseverance, sensation seeking, and positive urgency. Each item is rated using a 4-point Likert scale, ranging from 1 to 4: 1 (Agree Strongly), 2 (Agree Some), 3 (Disagree Some), 4 (Disagree Strongly). The questionnaire takes approximately 20 minutes to complete.

Liking Survey: Subjects will complete a validated, 100-item liking survey comprised of foods, beverages, physical activities, sedentary activities, pleasant experiences, and unpleasant experiences. The survey will take about 5–10 min to complete. Subjects will be oriented to the liking scale with examples of activities that are generally considered highly likeable (winning the lottery, succeeding), neutral (doing a routine chore), and highly dislikable (getting a paper cut, running out of money). The bidirectional, horizontal scale ranged from "strongest disliking of any kind" (-100) to neutral (0) and "strongest liking of any kind" (+100) labeled with five faces (Pallister et, 2015) Each item has a word label and a picture. The items are grouped into eighteen nutritional, sensory, or activity groups: alcohol, sweet foods, fruits, vegetables, low-fat

protein, high-fat protein, sweet drinks, fats, carbo- hydrates, whole grains, salty, bitter, sour, spicy/flavorful, physical activities, pleasant experiences, and unpleasant experiences [39]

Barrett's Impulsiveness Scale (BIS) [35]: The BIS is a measure of trait impulsivity that has been validated in both community and patient populations, particularly among those with externalizing disorders. The 30-item questionnaire can be reduced to six first-order factors: attention, motor, self-control, cognitive complexity, perseverance, and cognitive instability.

Yale Food Addiction Scale 2.0 (YFAS 2.0.) [34]: The YFAS 2.0 is a self-report questionnaire designed to assess the presence and severity of addictive-like eating. Items were adopted from diagnostic criteria for substance use disorders, and respondents are provided with a binary 'diagnosis' of food addiction, as well as severity ratings (none, mild, moderate, severe).

4.7 Dual energy x-ray absorptiometry (DXA)

DXA scans will be performed at baseline followed by weekly scans using the General Electric Lunar iDXA (General Electric; Milwaukee, WI, USA) to determine body composition. Participants will change into a hospital gown, remove all metal-containing objects and lie on a table while the scanner, which emits low energy X-rays, passes along the body. The scan will take approximately 10 minutes. The radiation dose per scan is less than 1 mrem, and therefore the total of 5 scans planned per subject is below the guideline of 5000 mrem per year allowed for research subjects by the NIH Radiation Safety Committee.

4.8 Physical activity monitoring

Physical activity will be quantified daily with an activity monitor using high sampling frequencies during all waking periods. Overall physical activity levels, daily changes, amount of time spent in sedentary, moderate, vigorous intensity categories and activity-associated energy expenditures will be extracted [25].

4.9 Oral glucose tolerance test

After an overnight fast, 75 grams of oral glucose will be administered. Blood samples will be obtained at 0, 10, 20, 30, 60, 90, 120, and 180 minutes to measure glucose, insulin, C-peptide, free fatty acid, and lactate concentrations. Blood samples for research will also be collected. If the results of this test indicate an abnormal blood glucose level consistent with potential diagnosis of diabetes, the subject will be informed by a physician on the research team prior to being discharged from the study. However, such abnormal results may not be revealed until the end of the study to avoid influencing eating behavior and risk compromising the primary aim of the study. Note that the planned experimental manipulation of diet composition can impact glucose tolerance. Therefore, an abnormal glucose tolerance test in the present experimental context need not necessarily indicate that the subject has impaired glucose tolerance in the absence of the experimental dietary manipulations.

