Dietary fat contains more than twice the calories per gram compared to carbohydrate and protein. Furthermore, foods with high amounts of carbohydrates also typically have high water content thereby reducing their energy density and making them more satiating compared with high-fat foods [1, 2]. Therefore, high-fat diets are thought to promote excessive calorie intake and weight gain. However, dietary carbohydrates have also been suggested to a play causal role in the pathological accumulation of body fat [3-6]. According to the "carbohydrate-insulin model" of obesity, an increased proportion of the diet with high-carbohydrate foods results in elevated insulin secretion that suppresses the release of fatty acids into the circulation and directs circulating fat towards storage. This decreased availability of fatty acids for use by metabolically active tissues such as heart, muscle, and liver is perceived as a state of cellular "internal starvation", leading to an adaptive increase in calorie intake [3, 6-9].

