While there is much debate surrounding the effect of diet composition on energy intake, most studies rely on self-reported measurements of diet which are known to provide inaccurate estimates of energy and macronutrient intake [10]. Furthermore, outpatient studies cannot ensure that subjects are exposed to only the diets under investigation and cannot adequately assess adherence. Only two previous studies have used objective methods to measure significant effects on ad libitum energy intake over 14-day periods between diets differing in fat (15-60% of total calories from fat) and diets differing in carbohydrate (27-67% of total calories from carbohydrate) [11, 12]. However, proponents of low-carbohydrate and low-fat diets often claim that the benefits of such diets require that the restricted macronutrient be limited to $\leq 15\%$ of total calories. Furthermore, the previous ad libitum feeding studies employed 3-day rotating menus with identical foods in each test diet. Thus, the limited variety of foods raises questions about ecological validity since the types of foods typically consumed on a low-carbohydrate, high-fat (LCHF) diet often differ widely from the foods consumed on a high-carbohydrate, low-fat (HCLF) diet. For example, LCHF diets typically employ a variety of animal products and avoid foods high in sugar and starch. In contrast, LFHC diets are often plant-based with most calories derived from high-starch foods and the use of cooking fats and spreads is restricted.

2. Study Objectives

In this study, we will investigate *ad libitum* food intake of 20 healthy adult volunteers who will each complete a 4-week stay at the NIH. During their stay, they will consume a LCHF diet and a LFHC diet for 2 weeks each, in random order. We will collect information (primary and exploratory endpoints detailed below) about energy intake and metabolic changes, in response to the two test diets. The test diets will be presented to subjects in amounts exceeding their daily energy requirements; subjects will be instructed to eat as much or as little of each diet as desired.

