This study will implement a pair of 7-day rotating menus for each test diet. The diets will be matched for presented calories and protein, but the LCHF diet will be low in carbohydrate (~10% of calories) and high in fat (~75% of calories) whereas the LFHC diet will be high in carbohydrates (~75% of calories) and low in fat (~10% of calories). The test diets will have a common foundation of vegetables with low amounts of digestible carbohydrates such as lettuce, spinach, kale, cabbage, cauliflower, zucchini, tomato, asparagus, broccoli, peppers, brussels sprouts, and green beans. The LCHF diet will add meat, poultry, fish, eggs, dairy, and nuts. The LFHC diet will add legumes, rice, root vegetables, soy products, corn, lentils, peas, whole grains, bread, and fruit. The diets will

be designed using a standard computerized nutrition database. Each subject will be admitted as an inpatient to the NIH Clinical Center and will stay on the 5SWN Metabolic Care Research Unit (MCRU).

Hypothesis: The hypothesis of this study is that the LCHF diet will lead to greater mean *ad libitum* energy intake as compared to a LFHC diet when the meals presented to the subjects are matched for daily calories and protein.

2.1 Primary Aims:

- 1. To determine differences in *ad libitum* energy intake (kcals) during 2 weeks of eating an LCHF diet as compared to 2 weeks of LFHC diet matched for presented calories and protein.
- 2. To determine differences in *ad libitum* energy intake (kcals) during the final week of eating a LCHF diet as compared to the final week of eating a LFHC diet matched for presented calories and protein.

The first primary aim maximizes the power to detect a significant effect whereas the second primary aim addresses the lack of an equilibration period upon transition to the first test diet from the pre-study period and the potential short-term carryover effect on the second test diet.

Previous studies have shown changes in glucose tolerance and insulin sensitivity after consuming diets that differ in their relative carbohydrate to fat content [13-18]. Hepatic triglyceride content can also be altered with isocaloric diet changes in as little as 9 days [19]. Therefore, we will explore changes in glucose tolerance, various inflammatory markers, energy expenditure, and body composition metrics as follows:

2.2 Exploratory Aims:

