4.10 Meal test

After an overnight fast, a liquid meal will be provided matching the macronutrient content of the prevailing diet and amounting to 30% of the estimated daily calorie requirements for weight maintenance as determined by 1.6×REE measured at screening. Blood samples will be obtained at 0, 10, 20, 30, 60, 90, 120, 180, 240, 300, and 360 minutes to measure glucose, lactate, free fatty acid, triglyceride, C-peptide, and insulin concentrations. Blood samples for research will also be collected.

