4.18 Daily Ketone Measurements

We may measure daily blood levels of beta-hydroxybutyrate using a hand-held device with a small quantity of blood (about 20 $\mu L)$ obtained by capillary sampling. We may also measure breath acetone levels using a handheld breathalyzer. Daily urine samples for ketone measurements may be collected. These measurements will allow for estimating the kinetics of onset and dissipation of nutritional ketosis when subjects transition to and from the low carbohydrate diet.

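### Does the 75 g glucose test in the last week of each diet call for special handling of those days in the final-week intake comparison (Aim 2)?

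*Combined protocol and SAP*

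**What the plan says.** Section 2.1 makes the final week of each diet the basis of the second primary aim, on the ground that "the second primary aim addresses the lack of an equilibration period upon transition to the first test diet from the pre-study period" and because of possible short-term carryover. Section 2 fixes the contrast: "the LCHF diet will be low in carbohydrate (~10% of calories) and high in fat (~75% of calories"), with the proportions roughly reversed for LFHC.

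Two tests sit inside that final week. Section 4.10 describes the meal test, in which "a liquid meal will be provided matching the macronutrient content of the prevailing diet and amounting to 30% of the estimated daily calorie requirements"; Appendix A marks it on days 11 and 25. Section 4.9 describes the oral glucose tolerance test (OGTT): "After an overnight fast, 75 grams of oral glucose will be administered". It is the same on either diet, and Appendix A marks it on days 13 and 27. Section 4.9 adds: "Note that the planned experimental manipulation of diet composition can impact glucose tolerance".

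Section 5 gives standard errors and detectable differences for 14 days and for the final 7 days. It does not say whether the test drinks count as ad libitum intake, and it plans no sensitivity analysis for the test days.

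**The concern.** The meal test follows the prevailing diet, but the glucose drink does not. On LCHF it about doubles the day's carbohydrate, or more; on LFHC it hardly alters the mix. Section 1 justifies such extreme diets by reporting the claim of their advocates that "the benefits of such diets require that the restricted macronutrient be limited to" 15% of calories or less, and the LCHF test day goes above that figure. Section 1 also sets out a theory in which high-carbohydrate eating raises insulin, "leading to an adaptive increase in calorie intake". A reader could therefore suspect that later eating responds to the drink differently on the two diets.

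The OGTT day and the day after are two of the seven days in Aim 2, the window meant to be the cleaner one. If the response did differ, part of the final-week contrast would reflect the test and not the diet, and no planned analysis would reveal it.

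**Working it through.** **Inputs.** From Section 5: day-to-day SD 500-600 kcal/d, 20 participants, zero within-subject correlation, 80% power, Type I error 0.05. From Section 4.9: 75 g glucose, taken as 75 × 4 = 300 kcal. From Section 2: carbohydrate about 10% (LCHF) and 75% (LFHC) of calories. Assumption not in the document: free intake E = 1.6 × REE with REE 1300-1900 kcal/d, so E = 2080-3040 kcal/d.

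**1. The plan's own figures.** The SD of a participant's diet difference is SD × √(2/days). The SE of the group mean is this divided by √20. For a two-sided paired t-test with 19 degrees of freedom, 80% power needs a difference of about 2.954 SE.
- 7 days: SE 59.8-71.7, detectable difference 176.5-211.8 kcal/d (stated: 175-210).
- 14 days: SE 42.3-50.7, detectable difference 124.8-149.8 kcal/d (stated: 125-150).

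Section 5 reproduces.

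**2. Change in diet composition.**
- LCHF carbohydrate on an ordinary day: 0.10E/4 = 52-76 g. The drink is 75/76 to 75/52 = 0.99 to 1.44 times that.
- LCHF share on the test day: (0.10E + 300)/(E + 300) = 21.3% to 18.1%.
- LFHC share on the test day: (0.75E + 300)/(E + 300) = 78.2% to 77.2%.
- LCHF share over the final week: (0.70E + 300)/(7E + 300) = 11.8% to 11.3%.

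The asymmetry on the day is real, but the week stays well under 15%.

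**3. Possible shift in the endpoint.** The 300 kcal is given once on each diet and cancels in the paired difference. A shift arises only if the fraction offset by eating less differs between diets by some amount d. It is then 300 × d/7 for Aim 2 and 300 × d/14 for Aim 1.

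| d | Aim 2 (kcal/d) | Aim 1 (kcal/d) |
|---|---|---|
| 0 | 0 | 0 |
| 0.25 | 10.7 | 5.4 |
| 0.50 | 21.4 | 10.7 |
| 1.00 | 42.9 | 21.4 |

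The last row needs full compensation on one diet and none on the other. It is 42.9/210 = 20% to 42.9/175 = 25% of the detectable difference. The 25% row is 10.7/71.7 = 0.15 to 10.7/59.8 = 0.18 of the SE of the estimate.

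**4. What a check without these days could show.** Leaving out two days gives 5 of 7, or 12 of 14. The reduced estimate is nested in the full one. With independent days the SE of their difference is SD × √[(2/20)(1/5 − 1/7)] = 37.8-45.4 kcal/d for Aim 2, and SD × √[(2/20)(1/12 − 1/14)] = 17.3-20.7 for Aim 1. With t = 2.093, chance alone spreads the Aim 2 difference over about ±79 to ±95 kcal/d.
- d = 0.25 would appear as 10.7/45.4 to 10.7/37.8 = 0.24 to 0.28 SE.
- d = 0.50 would appear as 0.47 to 0.57 SE.
- d = 1.00 would appear as 0.94 to 1.13 SE.

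Suppose instead that the drink changed appetite beyond its own calories. Each 100 kcal on both the test day and the next day moves Aim 2 by 100 × 2/7 = 29 kcal/d. To stand out from ±79 to ±95, the differential would have to be about 79 × 7/2 to 95 × 7/2, roughly 275 to 335 kcal on each of the two days.

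**The case for a change.** The best argument for a change is that it costs only wording, and that days dropped after seeing the data persuade nobody. Section 4.9 itself withholds abnormal OGTT results so as not to influence eating, so the authors saw the test as a possible threat to the primary aim. Section 3.3.2 also allows schedule changes that will not be reported, so the two tests might not stay balanced between windows.

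Part of this stands. Section 5 is silent, and a prespecified rule would be tidier than a later choice. The rest carries little weight.
- Section 4.9 guards against participants learning a result. It says that diet affects glucose tolerance, not that one drink alters energy intake differently by diet.
- The theory in Section 1 concerns an increased proportion of carbohydrate in the diet, and the 15% figure is an advocates' claim about the whole diet. Neither sets a daily limit for this trial.
- On scheduling, Section 3.3.2 places the OGTT at the end of each diet period, so it would have to move by about a week to leave one window. If that happened and the drink was counted as intake, one participant's difference would change by 42.9 kcal/d and the group mean by 42.9/20 = 2.1 kcal/d.
- A check leaving out the meal-test and OGTT days would drop a meal that is on-diet and keep the day after the OGTT, so it would not isolate the asymmetry. Any two-day omission also removes menu days whose foods differ between diets, so a discrepancy would be hard to read.

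Much of the information is collected anyway. Section 3.3.2 has leftovers weighed and snacks recorded, so daily intake can be re-examined. Section 4.18 foresees ketone measurements for "estimating the kinetics of onset and dissipation of nutritional ketosis when subjects transition to and from the low carbohydrate diet", and Appendix A lists urine and breath ketones daily.

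**Conclusion.** The observation is accurate: an off-diet glucose load falls in the final week of both diets, it is much further from LCHF than from LFHC, and Section 5 does not mention it. It does not call for a change. The primary analyses and stated detectable differences would stay as they are. Excluding the drink from intake cannot alter the diet contrast when it is given once on each diet. The plausible shift in Aim 2 is 11 to 21 kcal/d (43 at the extreme), of unknown direction and zero if compensation is equal; Aim 1 is half as exposed. A sensitivity analysis without these days has chance variation of 38-45 kcal/d (SE), so agreement would not show independence from the test days and modest disagreement would not show dependence.

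This rests on Section 5's assumptions (SD 500-600 kcal/d, independent days, 20 completers), an assumed free intake of 2080-3040 kcal/d for the composition figures, and a differential response limited to the drink's own 300 kcal for the 43 kcal/d ceiling. A larger effect on appetite cannot be sized from the document, and nothing in it points to one. Leaving the handling of test days to the analysts is a gap that they can fill sensibly from the daily records.
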